**D.4.4. Exclusion criteria:** 1. Unable to sign informed consent, 2. Contraindications to any of the components of the polypill, 3. Hemorrhagic stroke, 4. Severe cognitive impairment/dementia or severe global disability limiting the capacity of self-care, 5. Severe congestive cardiac failure (NYHA III-IV), 6. Severe renal disease, eGFR <30ml/min/1.73m^2), renal dialysis; awaiting renal transplant or transplant recipient, 7. Cancer diagnosis or treatment in past 2 years, 8. Need for oral anticoagulation at the time of randomization or planned in the future months, 9. Significant arrhythmias (including unresolved ventricular arrhythmias or atrial fibrillation) 10. Nursing/pregnant mothers, 11. Do not agree to the filing, forwarding and use of his/her pseudonymized data.

**D.4.5. Recruitment of study subjects:** A total number of 120 patients will be randomized (1:1) to treatment arms. Patients with stroke meeting inclusion/exclusion criteria will be recruited from the Family Medicine, Internal Medicine and Neurology outpatient clinics at KATH. Randomization will take place within 8 weeks of the index event (ischemic stroke) in a 1:1 ratio to one of the two arms: Polypill versus Usual care.

**D.4.6. Randomization Procedure:** Randomization of subjects in blocks of four will be conducted by a statistician ([name] PI) using a computer-generated random sequence of numbers. Consented participants will be assigned to either study arm at the baseline visit using the computer generated randomization sequence. The randomization sequence uses a minimization algorithm to ensure balance of prognostic factors such as stroke severity, average of 3 recorded baseline systolic BP measurements, & whether or not they are on background BP lowering agents, lipid modifiers & antithrombotic agents. Each sequence generated will be kept concealed in an envelope which will be opened by the Research Coordinator in the presence of the consenting study participant at enrollment.

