**D.4.7. Study protocol:** The diagnosis of stroke will be defined as an acute episode of focal cerebral, spinal or retinal dysfunction caused by infarction of central nervous system tissue, not resulting in death. Patients meeting eligibility criteria will be allocated to the experimental or active comparator arm. Patients allocated to the experimental arm will receive Two (2) (Polycap ®) taken orally once a day. Patients allocated to the usual care arm will receive standard of care therapies for secondary prevention with drugs and doses left at the discretion of the treating physicians. Patients assigned to Polypill will have their antihypertensive agents, lipid modifiers and anti-thrombotic agents withdrawn & replaced with the Polypill if they are already receiving such treatments before enrollment. Since our focus is to *isolate the effect of the polypill strategy itself & create equipoise*, at study inception providers for patients in both study arms will receive a brief one-time (Skype-based) training & a one time email synopsis on guideline recommended biomarker targets after stroke.

**D.4.7.1. Screening/run-in period-4 weeks:** All potentially eligible participants referred to or who contact the study team directly will undergo screening to determine eligibility using the pre-specified criteria (see Human Subject Protection document).

**D.4.7.2. Enrollment evaluation:** Information on stroke type from a cranial CT scan performed within 10 days of stroke symptom onset will be reviewed by the MPI ([name]), stroke subtype information where available will be sought to classify ischemic stroke using the TOAST classification into cardio-embolic, large-artery and lacunar ischemic stroke. Stroke severity and functional status at enrollment will be assessed using the modified NIHSS and Modified Rankin Score, followed by a detailed assessment of vascular risk factors namely hypertension, diabetes mellitus, dyslipidemia, cigarette smoking, cardiac diseases (atrial fibrillation, ischemic heart diseases, cardiomyopathies), from history and physical examination. Blood samples for baseline assessments of renal and liver function tests, lipid profile and HbA1C will be collected and contraindications for study medications assessed. All concomitant medications will be recorded in the case report form.

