CVD Risk Factor Control Tertiary/feasibility	1. Blood pressure control will be defined as Systolic BP <140 mmHg and/or diastolic DP <90mmHg or (>135/85mmHg in diabetes patients). Mean change in SBP at month 12 from baseline will be compared in the two treatment groups. 2. Dyslipidemia: control will be defined by change in mean LDL-cholesterol <100mg/dl or <70mg/dl. Mean change in LDL-C at month 12 from baseline will be compared in the two treatment groups.
Incidence of Adverse events Tertiary/feasibility	1. Recurrent stroke: fatal/ severely disabling stroke or non-fatal stroke; Coronary Artery Disease: Acute STEMI/NSTE deaths 2. Re-hospitalization for any CV cause; All-cause mortality

**D.4.9. Sample size justification:** The end of study CIMT value will be subtracted from the baseline CIMT value and divided by the length of follow-up. The rate of change in CIMT (mm/yr) between treatment arms will be tested with a two sided t-test. The rate of change in common CIMT in treated patients is around 0.085 mm/yr with a standard deviation of 0.035. We assume that polypill improvement leads to a halting of CIMT progression with an assumed rate of change of 0.0825 mm/yr. With a two sided alpha of 0.05 and a 90% power we need 82 patients (104 patients with 20% drop-out rate).

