**D.4.10. Statistical analysis plan:** Prior to addressing each hypothesis, univariate descriptive statistics and frequency distributions will be calculated as appropriate for all biological variables (including gender, age) comparing individuals by treatment arms (Polypill arm vs usual care arm). Briefly, box plots will be used to examine the relative distribution of variables stratified by treatment arm. Non-parametric and equivalent parametric statistics will be utilized to compare groups. Appropriate regression models (linear regression for continuous outcomes such as carotid-media thickness; Cox-proportional hazards regression for time to event measures such as recurrent strokes, CVD events, deaths and defaults) will be used to estimate the association of covariates with each outcome. When building models for each specific aim, the first stage of the model building algorithm will involve testing if the individual covariates are correlated with the main outcome variables. A liberal alpha=0.20 will be used for these unadjusted analyses. Once the initial pool of candidate predictors has been identified, regression models consisting of multiple covariates will be fitted to identify potential confounders and effect modifiers. To achieve unbiased and robust results, optimal combinations of predictors, including interaction effects, will be identified and used for further analysis based upon whether or not they are a confounder, by whether they did not improve the model fit, or increased the standard error of the parameter estimate of the primary covariates. Finally, each model will be rigorously assessed for collinearity and goodness of fit using residual analysis. Model diagnostics will be performed using tools (in SAS or STATA) that detect outliers and influential data points. We will use diagnostic measures such as residual deviance, the hat matrix diagonal and residual chi-squared deviance and the difference between chi-square goodness-of-fit when an observation is deleted. Plots of these against predicted values will be used to investigate the influence of each data point on the model. We will handle missing data using several techniques including multiple imputation and propensity score methods.

**D.4.11. Data Safety Monitoring Board (DSMB):** A DSMB comprised of three experienced external experts will meet twice per year to review the safety, ethics, and outcomes of the study.

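### D.4.6 describes one randomization sequence as both blocks of four and minimization; one scheme should be kept and its balancing factors fixed in the CIMT analysis

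*Combined protocol and SAP*

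**What the plan says.** D.4.6 (Randomization Procedure) makes three statements about a single sequence.

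- It is blocked: "Randomization of subjects in blocks of four will be conducted by a statistician", from computer-generated random numbers.
- It is minimized: "The randomization sequence uses a minimization algorithm to ensure balance of prognostic factors such as stroke severity". The other factors are the "average of 3 recorded baseline systolic BP measurements" and whether the patient already takes blood-pressure, lipid or antithrombotic drugs. The list is introduced as examples, and no factor levels, weights or random element are given.
- It is held in envelopes: "Each sequence generated will be kept concealed in an envelope which will be opened by the Research Coordinator", with the consenting participant present.

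On when the factors become known, D.4.7.2 says: "Stroke severity and functional status at enrollment will be assessed using the modified NIHSS".

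On the analysis, D.4.9 says: "The rate of change in CIMT (mm/yr) between treatment arms will be tested with a two sided t-test". No covariate is named there. D.4.10 plans "linear regression for continuous outcomes such as carotid-media thickness", with covariates first screened one at a time against the outcome: "A liberal alpha=0.20 will be used for these unadjusted analyses". It neither names the allocation factors nor requires them in the model.

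**The concern.** A blocked list and sealed envelopes go together: the list exists before anyone is enrolled and takes no account of who the patients are. Minimization works the other way. Each assignment depends on the new patient's factors and on the running totals in each arm, so it has to be computed patient by patient. D.4.6 claims both for one sequence and describes no combination, such as blocks within strata, that would reconcile them.

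Two things follow. A reader cannot tell which scheme will be used, and so whether the stated balance on severity, blood pressure and prior drugs is designed or left to chance. And the analysis is not matched to the allocation: if the factors do steer allocation and also predict CIMT change, a t-test that omits them uses too large a standard error.

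**Working it through.** **1. Do the two schemes coincide?** A blocked list splits every consecutive four patients 2:2. In 3,000 simulated trials per setting of 120 patients, minimized with an assumed 0.8 probability of the balancing arm, none had all 30 consecutive fours split 2:2. Blocked lists always do.

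**2. Balance if the envelopes hold a block list.** Inputs: 120 patients, 1:1 (D.4.5). For a binary factor with prevalence p, the between-arm difference in counts has SD √(120·p(1−p)), and its mean absolute value is about 0.798 times that.

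| p | SD | Mean difference |
|---|---|---|
| 0.50 | √30.0 = 5.48 | 4.4 |
| 0.65 | √27.3 = 5.22 | 4.2 |
| 0.70 | √25.2 = 5.02 | 4.0 |
| 0.90 | √10.8 = 3.29 | 2.6 |

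The last three prevalences are proxies from C.3 (antithrombotic use, statin use, hypertension). The two drug rates are from one year after stroke, not from enrollment. Simulation agrees and gives a 95th percentile of 11 at p = 0.50. Minimization at 0.8 gives 1.4 to 1.5, with a 95th percentile of 4.

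**3. Type I error if minimization is used.** Let R² be the share of variance in CIMT change that the factors explain. The documents give no value; 10% to 30% is assumed. Under perfect balance the true variance of the arm difference is (1−R²) times what the t-test assumes, so true alpha is 2·[1−Φ(1.96/√(1−R²))]. The simulation used 0.8 minimization on five independent binary factors, with 20,000 runs and a Monte Carlo SE of about 0.15 points.

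| R² | 1.96/√(1−R²) | Alpha, perfect balance | Simulated t-test, 120 analysed | Simulated t-test, 96 analysed |
|---|---|---|---|---|
| 10% | 2.066 | 3.9% | 3.9% | 4.2% |
| 20% | 2.191 | 2.8% | 3.0% | 3.5% |
| 30% | 2.343 | 1.9% | 2.3% | 2.9% |

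A model with the five factors fixed gives 4.9% to 5.0%. Under blocks the t-test stays at 5.1% to 5.3%.

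**4. The effect size used for power.** The rates in D.4.9 differ by 0.085 − 0.0825 = 0.0025 mm/yr. Divided by the SD of 0.035, that is 0.07 SD. The usual formula, 2(1.96 + 1.2816)²·(0.035/0.0025)², gives about 4,119 per arm, so the stated total of 82 is not reproduced. With 41 per arm, 90% power corresponds to 0.725 SD. That mismatch is a separate matter. It is shown here only because the power figures below use 0.725 SD.

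**5. Power with 82 analysed** (10,000 runs, same factor assumptions).

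| R² | Minimization, t-test | Minimization, fixed factors | Blocks, t-test | Blocks, fixed factors |
|---|---|---|---|---|
| 0% | 90.0% | 89.1% | 89.7% | 87.8% |
| 10% | 90.7% | 92.2% | 89.8% | 90.8% |
| 20% | 91.5% | 94.7% | 89.6% | 93.6% |
| 30% | 92.2% | 97.0% | 89.6% | 96.1% |

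**6. Predictability.** Over the six orders of a block of four, 8 of 24 assignments are certain given all earlier ones (33.3%), and the best guess is right in 17 of 24 (70.8%). The 33.3% is an upper bound: it needs the block size and every earlier assignment to be known. If each earlier assignment is seen with probability one half, it falls to 8.3%.

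**The case against.** **The procedure may be feasible.** D.4.6 never says the envelopes are filled in advance. Assignment happens at the baseline visit, after a screening/run-in period, so a per-patient result could be placed in an envelope. This stands in part. A reader might infer that D.4.6 is impossible to carry out; the text supports only that its two descriptions do not fit one sequence and that no per-patient step is given.

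**The t-test is safe.** After minimization it errs on the cautious side, and its power stays at or above the planned 90% in these illustrations. This stands. A reader might infer that adjustment is needed to protect against false positives. It is not: alpha falls below 5%, and the loss is of efficiency. Under blocks, even the nominal level is not at issue.

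**The primary test is identifiable.** A reader might infer that the plan leaves the primary analysis open between t-test and regression. Table 1 makes the rate of change the primary outcome and D.4.9 assigns it the t-test, so the t-test is the natural reading. What remains is that neither section fixes the allocation factors.

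**Screening would do nearly as well.** If all five factors were candidates in D.4.10, alpha would be about 5% and power at most 1 point below the fixed model. True, but D.4.10 does not guarantee that they are candidates, and it selects the model from the outcome data.

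**Chance imbalance is ordinary.** A difference of 4 or 5 patients between arms of 60 is already covered by the t-test's error rate. This also stands; the complaint is that the protocol says balance is ensured.

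**Conclusion.** The contradiction in D.4.6 is real and should be resolved. Its statistical consequence is moderate. Under a block list, promised balance is not delivered. Under minimization, the t-test runs at about 4% to 2% instead of 5% and gives up roughly 1.5 to 5 points of power against a model with the factors (90.7% versus 92.2% at R² 10%; 92.2% versus 97.0% at 30%).

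These sizes rest on assumed R² values, an assumed 0.8 random element, five independent binary factors (severity and systolic pressure are not binary, and the drug indicators may be correlated), and a 0.725 SD effect that the stated rates do not support. The direction does not depend on the exact values; the amounts do.

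A reader might also infer that allocation was foreseen and the result biased. The trial is open label and single centre, the block size is printed in the protocol, and the Research Coordinator sees assignments as envelopes are opened. But the documents do not say that this person also selects patients, envelopes are opened for consenting participants, and D.4.7.5 blinds the sonographers. No bias is shown.

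**What to change.** In D.4.6 keep one scheme and delete the other.

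- **(a) Minimization.** Compute it per patient, state the closed list of factors with their levels and a random element, and release the arm only after consent and baseline factors are recorded. This needs a short script run at each enrollment. No assignment is certain, but guessing is not eliminated: 76% to 77% success if all five factors are tracked, 64% from arm totals alone.
- **(b) Permuted blocks.** Drop the minimization claim and do not disclose the block size to recruiting staff. This needs no system but gives up designed balance. Varying the size (4 and 6, for example) cuts certain predictions from 33% to about 5%, yet best-guess success only moves from 71% to 69%, so it should not be presented as solving predictability.

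In D.4.9 and D.4.10, make the primary CIMT comparison one linear model with arm, severity, systolic pressure and three background-drug indicators fixed in advance, replacing the unadjusted t-test and the 0.20 screening for this comparison. Under (a) this restores the nominal level and gains precision if the factors are prognostic. Under (b) it is a precision gain only.

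The cost is a short amendment and no new data. If the factors predict nothing, power drops by 1 to 2 points: 90.0% to 89.1% under minimization, 89.7% to 87.8% under blocks.

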
#### D. APPROACH

**D.1. Overview:** The overarching objective of the Stroke Minimization through Additive Anti-atherosclerotic Agents in Routine Treatment (SMAART) trial is to assess whether a polypill containing fixed doses of 3 antihypertensives, a statin and antiplatelet therapy taken once daily orally would result in carotid intimal thickness regression, improved adherence, and tolerability compared with 'usual care' group on separate individual secondary preventive medications among Ghanaian first time stroke survivors. Our ultimate objective is to design of a future multi center, double-blinded, placebo-controlled, parallel-group, RCT comparing the clinical efficacy of the polypill strategy vs 'usual care' in the African context to derive locally relevant, high-quality evidence for routine deployment of polypill for CVD risk moderation among stroke survivors in LMICs.

**D.2. Design:** SMAART incorporates (i) a pilot randomized controlled trial and (ii) a human capital/institutional capacity building component. We propose a randomized, open label, blinded endpoint clinical trial with the intervention arm assigned to a polypill containing 3 antihypertensives, a moderate/high-intensity statin and Aspirin to be taken orally, once daily in the form of two hard capsules compared with the 'usual care' arm who will continue to take separate, individual secondary preventive medications as prescribed by their physicians. We will assess CIMT changes as a robust intermediary outcome measure for CVD events, adherence, tolerability, and risk factor control rates. Furthermore, a cadre of emerging investigators from Ghana will benefit from the rich

learning environment to be created through the implementation of the RCT and the interactions (2 years) with experts from the Medical University of South Carolina.

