#### **D.4. SMAART (Specific Aims 1 and 2):**

- To evaluate whether a polypill-based treatment strategy vs. usual care will result in carotid intimal media thickness stabilization/regression among recent stroke patients at one year after an index ischemic stroke. (Aim 1)
- To evaluate whether a polypill-based treatment strategy vs. usual care will improve vascular risk reduction drug adherence and tolerability among recent stroke patients at one year after an index ischemic stroke. (Aim 2)

**D.4.1. Study Design:** SMAART is a phase II randomized, open label, blinded endpoint clinical trial to evaluate the effect of a polypill taken once daily orally in improving CMIT regression and adherence to secondary risk reduction drug intake vs. 'usual care' group with separate individual secondary preventive medications among Ghanaians with recent onset stroke/TIA in a single center study.

**D.4.2. Participants:** The participants will include 120 adult Ghanaian recent stroke/TIA patients (within two months of stroke onset) meeting inclusion/exclusion criteria who will be randomly assigned to either intervention or usual care arms.

**D.4.3. Inclusion Criteria:** 1. Above the age of 18 years; male or female; 2. Stroke/TIA diagnosis no greater than two months before enrollment. Ischemic strokes including lacunar, large-vessel atherosclerotic, cardio-embolic subtypes are eligible 3. Subjects with stroke may present with at least one of the following additional conditions: Documented diabetes mellitus or previous treatment with oral hypoglycemic or insulin; documented hypertension >140/90mmHg or previous treatment with anti-hypertensive medications; Mild to moderate renal dysfunction (eGFR 60-30ml/min/1.73m^2); Prior myocardial infarction 4. Legally competent to sign informed consent.

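### If the fixed block of four in D.4.6 is used, an expected one third of assignments in this single-centre open-label trial can be known in advance; the minimization named in the same section must first be reconciled with it.

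*Combined protocol and SAP*

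**What the plan says.** **Method.** D.4.6 (Randomization Procedure) states "Randomization of subjects in blocks of four will be conducted by a statistician", using a computer-generated list. D.4.5 gives the ratio and number: "A total number of 120 patients will be randomized (1:1) to treatment arms". Only one block size is given, and nothing is said about varying it or withholding it from site staff. D.4.6 then says the sequence works by minimization on prognostic factors such as stroke severity, mean baseline systolic pressure and background treatment. It gives no weights, cut-points or random element, and does not say how minimization combines with blocks or with envelopes.

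**Concealment.** "Each sequence generated will be kept concealed in an envelope", and that envelope is "opened by the Research Coordinator in the presence of the consenting study participant at enrollment". Consent comes before assignment: "Consented participants will be assigned to either study arm at the baseline visit using the computer generated randomization sequence".

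**Setting.** D.2: "We propose a randomized, open label, blinded endpoint clinical trial". D.4.1 places the trial "among Ghanaians with recent onset stroke/TIA in a single center study".

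**Not stated.** The plan does not say who approaches, screens or enrols patients, where the envelopes are kept, whether they are opaque, sealed and numbered, whether site staff know the block size, or whether a patient's entry is irrevocably recorded before an envelope is opened.

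**The concern.** An envelope hides an assignment only if its content cannot be worked out from earlier ones. With a fixed block of four at 1:1, the last place in a block is always determined, and the third is determined whenever the first two match. Open-label treatment at one centre makes past assignments visible, and one role opens the envelopes.

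The plan leaves room to act on such knowledge. Randomization may take place at any time within 8 weeks of the event (D.4.5), after a screening period of 4 weeks (D.4.7.1). At the expected 5 cases per week (section E), a block of four fills in 4/5 of a week, so moving a patient by one or two places takes days and breaks no stated rule. Some exclusions call for judgement, such as contraindication to a polypill component or anticoagulation planned for later (D.4.4). Staff may also prefer one arm for a given patient, because background preventive drugs are replaced in the polypill arm, while usual care stays at the physician's discretion (D.4.7).

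At stake is the comparability of the arms for CIMT change, tolerability and clinical events. The regression adjustment in D.4.10 cannot correct selection on features that were not recorded.

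**Working it through.** The plan gives no predictability figure, so there is none to reproduce.

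**Inputs.** Block size 4 (D.4.6); ratio 1:1 and N = 120 (D.4.5), hence 120/4 = 30 blocks; open label (D.2, D.4.1); one centre (D.4.1). Assumptions: one unstratified list, and an observer who knows the block size and all earlier assignments.

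**Certain assignments.** There are C(4,2) = 6 equally likely blocks with two places per arm.
- Places 1 and 2 are never certain.
- Place 3 is certain if places 1 and 2 match: 2 of 6 blocks, probability 1/3.
- Place 4 is always certain.

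The expected share is (0 + 0 + 1/3 + 1)/4 = 1.333/4 = 33.3%, and 30 × 1.333 = 40 of 120. Each block has one or two certain places, so the possible range is 30 to 60. The SD is √(30 × 1/3 × 2/3) = 2.6. Simulation gave 33.4%.

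**Best guess.** The observer always guesses the arm that is behind in the current block.
- Place 1: 1/2.
- Place 2: 2/3.
- Place 3: 1/3 × 1 + 2/3 × 1/2 = 2/3.
- Place 4: 1.

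The sum is 0.5 + 0.667 + 0.667 + 1 = 2.833, and 2.833/4 = 70.8%, against 50% by chance. Simulation gave 70.8%.

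**If the blocks were stratified.** The plan states no strata. Assuming equal strata, each followed by the observer, with N = 120:

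| Strata | Certain in advance |
|---|---|
| 1 | 33.3% |
| 4 | 31.9% |
| 8 | 30.6% |
| 16 | 27.8% |
| 32 | 22.1% |

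**If block sizes vary.** Simulation, assuming sizes drawn with equal chance and an observer who knows the set of sizes but not where blocks begin and end, with N = 120:

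| Sizes | Certain | Best guess correct |
|---|---|---|
| 4 only | 33.3% | 70.8% |
| 4, 6 | 5.5% | 69.2% |
| 4, 6, 8 | 2.1% | 68.0% |

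Varying the size removes most of the certainty but little of the guessing advantage.

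**Under minimization.** No share can be computed, because the random element, weights and cut-points are not given.

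**The case against.** **The method is not settled.** D.4.6 names minimization as well as blocks, and the method decides the number. This stands: the one-third figure is conditional on the block reading. That reading fits envelopes prepared beforehand better, since minimization needs each patient's factors at entry. Minimization is not a safeguard as written, because a version without a random element can be predicted by someone who knows the earlier patients' factors.

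**Safeguards exist.** Patients consent before assignment, the envelope is opened in front of them, and screening uses criteria set in advance (D.4.7.1). These limit swapping once an envelope is open. They do not govern whom to approach, or when. The blinded sonographers (D.4.7.5) protect the CIMT measurement, not the make-up of the arms.

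**Stronger readings that the documents do not support.**
- A reader might infer that the coordinator both enrols patients and opens the envelopes, or that the envelopes sit in the recruiting clinics. D.4.6 says only that the coordinator opens them at enrolment. D.4.7.1 refers to a separate human-subject document for the eligibility criteria, so silence here on roles is weak evidence.
- A reader might infer that site staff know the block size because it is printed. Whether they see this text is not stated.
- A reader might take 33% or 71% as the amount of bias. Both measure predictability. No size or direction of effect on CIMT follows from them. Moreover, systolic pressure and stroke severity are named balancing factors, and severe global disability is an exclusion (D.4.4), so selection on those features is a weak example.
- Read literally, one envelope might hold a whole block's sequence, so that up to 3 of 4 assignments would be known once it was opened. The wording may equally mean one assignment per envelope.

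**Conclusion.** The point holds in conditional form. With a fixed, unstratified 1:1 block of four, an expected 40 of 120 assignments (33%) are certain in advance and 71% can be guessed correctly. This assumes someone who knows the block size, can follow earlier open-label assignments and can influence enrolment. The documents make the second condition plausible and leave the other two open. They show a vulnerability to selection bias, not that bias has occurred or how large it would be. Under minimization the one-third figure does not apply, and predictability cannot be assessed until the algorithm is specified. The procedure should be corrected before enrolment, because selection cannot be undone afterwards.

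**What to change.** State in D.4.6 which allocation method is used, and delete or reconcile the other. Then, in order of importance:

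1. **Release after registration.** The statistician's office holds the list and releases each assignment by phone or email. Release follows only once the patient's ID, consent, confirmed eligibility and baseline data are logged in a record that cannot be deleted. Every registered patient is kept in the analysis as randomized; the patient's right to withdraw is unaffected. D.4.6 marks the statistician as a PI, so the plan should confirm that whoever holds the list takes no part in recruitment.
2. **If blocks are kept,** draw the sizes at random (for example 4, 6, 8) and keep them out of site documents. On the assumptions above, this cuts certain assignments from 33% to about 2% but guessing accuracy only from 71% to about 68%, so it supports step 1 and does not replace it.
3. **If minimization is kept,** compute it centrally at registration with a random element (for example 0.8 probability of the favoured arm), and state the factors, cut-points and weights.

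**Cost.** Protocol wording, a short wait for each assignment, and some availability of the statistician, which the documents do not describe. With a largest block of 8, the final imbalance is at most 4 patients, reached if the trial ends with the first four places of such a block all in one arm.
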